## 6.2 Methods

### 6.2.1 Study Design

This study will be implemented with a convenience sample of 4 pediatric primary care practices. Two will be randomly assigned to receive the intervention and two will serve as the comparison groups. Two of the practices will be located at UF Health in Gainesville and two will be located at UF Health in Jacksonville. The control group will provide their usual care related to tobacco and nicotine product use screening and cessation recommendations. The control group will be given the opportunity to participate in the intervention following study completion.

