Practices will be asked to identify a location in the waiting room or an exam room where the screening tool can be completed without the parent present. Completing the tool is expected to take 10 minutes of the youth's time and 10 minutes of the parent's time, inclusive of the time to complete the informed consent. We estimate practices will need to participate in the project for approximately 6 months. This time period includes baseline and follow-up data collection, study implementation, and participant accrual. The 6-month time period is also necessary for those practices who wish to use the project for participation in their Maintenance of Certification (MOC) requirements.

The total duration of study participation for the practices is estimated to be 10 months. This includes a 3-month start up period, a 6-month intervention (or control) time period and a 1-month follow-up. The 6-month intervention period is necessary for those practices who want to use the study participation to assist them in meeting their MOC requirements. For practices not participating in the MOC Program, the intervention period is finished when 20 patients complete at least the “advise” and “assess” components.

Practices can make some modifications to the intervention to fit with their workflow. For example, some practices have nursing staff screen for tobacco/nicotine use and make recommendations about cessation strategies. Other practices have physicians provide the screening and counseling. Practices can make adaptations regarding who administers the 6As but they must follow the 6A intervention. Any type of primary care visit can be used to conduct the 6As.

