D. Parent Brief Questionnaire (PBQ – Appendix D): The PBQ was developed using questions recommended by the American Academy of Pediatrics. Parents are one of the most important sources of a child's tobacco smoke exposure. Therefore screening parents is a recommended best practice. The PBQ will also be administered using ResearchACTS.

E. 6As and Best Practices Medical Record Review Form (6As MRR - Appendix E): At baseline, we will request the (Medical Record Number) MRN from the Integrated Data Repository (IDR) for 75 randomly selected patients from both control and intervention practices in Gainesville and Jacksonville, which will be reviewed for 1) adherence to the 6As (through whichever number of steps are applicable for that patient) inclusive of tobacco and nicotine product use and 2) parental screening for tobacco use. Specifically, the IDR will be asked to select MRNs from 75 records consecutively from well care visits from participating providers for patients 11 through 17 years of age from the 6 months prior to the start of the study until they reach 75 records. OneFlorida has a medical record review team with certified medical record coders. The medical record review team will measure compliance with the 6As and parental screening using the review tool. At the end of the intervention period, we will request the medical records for those patients participating in the intervention. We will request MRNs from the IDR for control group practices and review 75 consecutive medical records for patients ages 11 through 17 years seen during the 6 month study period.

[name] will train the medical record reviewers for the Gainesville and Jacksonville sites. Interrater reliability will be established and training will continue until there is 98% agreement between reviewers. During the record review process, [name] will be available to the reviewers to respond to questions. If there is not 98% agreement among the medical record reviewer findings, the medical record reviewers will undergo additional training from [name]..

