### 6.2.5 Analysis Plan

Intervention effect on clinician adherence to the 6As: The primary outcome is clinician adherence to the 6As inclusive of tobacco and nicotine product use as collected in the medical records. During both the baseline and follow-up periods, we will request and review medical records to identify the following primary outcome measures: discussion of patient’s tobacco use, advice to quit, and discussion of parent’s tobacco use. Since this is a pre-post design with one intervention group and one control group, we will perform ANCOVA-type analyses assuming that the patients and providers are independent of each other. For each outcome, we will fit a logistic regression model in which the dependent variable is the post-intervention measure of the outcome. The main independent variables will be the pre-intervention measure of the outcome, group (binary: intervention vs. control), and pre-intervention measure by group interaction. In all models, we will also control for age, gender, and race, and clinic (multi-nominal: clinics 1-4). The model building process will follow guidelines provided by Hosmer and Lemeshow.

Intervention effect on practice characteristics: Practice characteristic data will be measured from the Change Process Capability Questionnaire and the Adaptive Reserve Questionnaire (Appendix B). We will collect the practice characteristic data twice, once at baseline and once at 9 months. Therefore, we will fit ANCOVA models for data analysis, assuming the practices are independent of each other. The characteristics include meeting frequency, clinician/staff performance evaluation, and planned communication. The primary predictor of interest is group (intervention vs. control). The model building process will follow guidelines provide by Muller and Fetterman. We will perform residual analysis to check the normality assumption of the models. We will perform box-cox transformation if there is a violation of the normality assumption.

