**Appendix E. Pediatric Primary Care Tobacco/Nicotine Best Practices Screening Tool**

*(Response options: Met? Yes or No)*

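### The primary model contains both group and clinic although whole practices are randomised, so the group effect cannot be estimated; its pre-intervention covariate is also undefined

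*Combined protocol and SAP*

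**What the plan says.** Section 6.2.1 describes four practices: "Two will be randomly assigned to receive the intervention and two will serve as the comparison groups". The practice is the unit assigned, so every patient and provider in a practice is in the same arm.

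Section 6.2.5 names three primary outcome measures taken from medical records: discussion of the patient's tobacco use, advice to quit, and discussion of the parent's tobacco use. Each gets a logistic regression with the post-intervention measure as the dependent variable. The plan states: "The main independent variables will be the pre-intervention measure of the outcome, group (binary: intervention vs. control), and pre-intervention measure by group interaction". It then adds: "In all models, we will also control for age, gender, and race, and clinic (multi-nominal: clinics 1-4". Patients and providers are assumed independent, and no random effect for clinic is mentioned.

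Section 6.2.3, item E, says where the records come from:
- Baseline: 75 records, drawn from this pool: "well care visits from participating providers for patients 11 through 17 years of age from the 6 months prior to the start".
- Follow-up, intervention practices: "At the end of the intervention period, we will request the medical records for those patients participating in the intervention".
- Follow-up, control practices: the team will "review 75 consecutive medical records for patients ages 11 through 17 years seen during the 6 month study period".

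No section links a follow-up chart to a baseline chart, or defines the pre-intervention measure as a provider or clinic rate.

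**The concern.** Two features of the model conflict with the design.

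First, if each clinic lies in one arm only, a model with all clinic differences already in it has nothing left from which to estimate a separate group effect. Software would drop group, drop a further clinic so that group becomes a comparison of one intervention clinic with one control clinic, or return one of infinitely many equivalent solutions. The plan does not say which quantity would be reported, so the odds ratio for each primary outcome is not fixed before the data are seen.

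Second, an ANCOVA-type model needs a baseline value for every follow-up record. With separately drawn charts, a patient has one only if that patient also fell in the baseline draw.

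**Working it through.** The plan gives no effect size, expected rate or power figure for the primary outcome, so there is no stated number to reproduce. The check concerns estimability.

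**Aliasing.** Let C1 and C2 be the indicators of the intervention clinics, and C3 and C4 those of the control clinics. Then group = C1 + C2 exactly, and C1 + C2 + C3 + C4 = 1 (the intercept). Columns against rank of the design matrix, before age, gender and race:

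| Model | Columns | Rank | Group estimable |
|---|---|---|---|
| Intercept, group, 3 clinic dummies | 5 | 4 | no |
| plus pre and pre-by-group, patient-level pre | 7 | 6 | no |
| plus pre and pre-by-group, provider-level pre (2, 3, 4 or 8 providers per clinic assumed) | 7 | 6 | no |
| plus pre and pre-by-group, clinic-level pre | 7 | 4 | no |

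The result is the same for all six ways of choosing two of four practices, and for different chart counts. It therefore does not matter whether the 75 in section 6.2.3 means per practice or in total.

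If the clinic baseline rate is used, then even without clinic terms the intercept, pre, group and pre-by-group are four parameters for four distinct practice values, and the model is saturated. A provider-level rate avoids this.

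**What would be printed.** The documents give no follow-up rates, so these are assumed: 80% and 60% in the intervention clinics, 48% and 36% in the control clinics. Pre and pre-by-group are left out to keep the illustration simple. Odds = p/(1 − p):
- 0.80/0.20 = 4.000 and 0.60/0.40 = 1.500
- 0.48/0.52 = 0.923 and 0.36/0.64 = 0.5625

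Group odds ratio by choice of reference pair:
- 4.000/0.923 = 4.33
- 4.000/0.5625 = 7.11
- 1.500/0.923 = 1.62
- 1.500/0.5625 = 2.67

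All four codings fit the data identically. A minimum-norm solver gives 3.33, 1.60, 1.92 or 2.67, depending on which clinic dummy is omitted. Two quantities that do not depend on the coding, neither of them specified in the plan, are:
- pooled arms: (0.70/0.30)/(0.42/0.58) = 3.22
- average two-versus-two contrast: √[(4.000 × 1.500)/(0.923 × 0.5625)] = 3.40

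The ratio of largest to smallest equals the product of the two within-arm clinic odds ratios: (4.000/1.500) × (0.923/0.5625) = 4.38 = 7.11/1.625.

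**Range over the assumption.** Arm means are held at 70% and 42%:

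| Gap between clinics within each arm | Group OR by reference pair |
|---|---|
| 0 points | 3.22 only |
| 5 points | 2.59 to 4.04 |
| 10 points | 2.09 to 5.11 |
| 20 points | 1.38 to 8.50 |

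With no effect (40% in both arms) and a 10-point gap, the clinics are at 45% and 35%, with odds 0.818 and 0.538. The range is 0.538/0.818 = 0.66 to 0.818/0.538 = 1.52, so even the direction depends on coding.

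**The alternative model.** Stack baseline and follow-up charts with an intercept, 3 clinic dummies, period and period-by-group: 6 columns, rank 6. Adding age, gender and a five-level race variable gives 12 columns, rank 12. Period-by-group is estimable, and no patient linkage is needed.

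**The case against.** The aliasing itself has no answer in the text. Clinic is to be in all models, so model building cannot remove it, and a random clinic effect is not described. The arguments on the other side concern scope and remedy.

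- *The odds ratios are illustrative.* This is correct: the rates are assumed, and the planned pre terms are left out. With the interaction kept, the group coefficient would mean the effect at pre = 0, and any two-versus-two contrast would depend on the pre value chosen. That is a further quantity the plan would have to define.
- *A baseline measure could be built.* Record numbers are requested, so linkage is possible. The outcome is clinician adherence and baseline charts come from participating providers, so a provider rate is a natural reading. But the plan states neither, and group stays aliased under both.
- *Smaller repairs exist.* Removing the clinic term makes group estimable under all three readings of pre. It still needs a defined pre measure and leaves clustering ignored: with 75 charts per practice and assumed intraclass correlations of 0.01, 0.05 and 0.10, the design effect 1 + 74 × ICC is 1.74, 4.70 and 8.40. Pre-specifying a two-versus-two contrast is another option, again only once pre is defined.
- *Full rank does not guarantee a stable fit.* If advice to quit is scored only in users (an assumption), 75 charts at the 4.3% to 11% prevalence in section 6.2.2 yield about 3 to 8 users per practice. Separation is then a real risk for that outcome.
- *This is a pilot with no stated alpha or power.* True, but Aim 2 is to gather effectiveness data, and this is the model planned for it. Choosing the repair after seeing the data would be post hoc.

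**Conclusion.** The point holds and must be fixed. As written, the primary model cannot estimate the group coefficient for any of the three outcomes, under any reading of the pre-intervention measure. This is exact algebra and rests only on whole-practice assignment and a four-level fixed clinic term. The pre-intervention measure is, in addition, undefined for separately drawn charts.

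The size of the consequence depends on how much clinics within an arm differ, which the documents do not say. The ambiguity vanishes only if they do not differ at all.

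**What to change.** Replace the primary model in section 6.2.5 with a logistic regression on the stacked baseline and follow-up charts: outcome on clinic (four levels), period, period-by-group, age, gender and race. Name the period-by-group term as the intervention effect. Delete the pre-intervention measure, its interaction and the group main effect. The sentence assuming independent patients and providers should go too, since it conflicts with point 2 below.

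State two limits in the plan.

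1. *Comparable samples.* Baseline charts are well-care visits. Intervention follow-up charts are those of participants, and section 6.2.2 allows that "Any type of primary care visit can be used to conduct the 6As". Control follow-up charts have no stated visit type. Suppose there is no effect, documentation is 60% at well-care and 40% at other visits, baseline is all well-care, and the follow-up well-care share is 80% (intervention) and 50% (control), all assumed. Follow-up rates are then 0.8 × 0.60 + 0.2 × 0.40 = 56% and 50%, and the period-by-group OR is (0.56/0.44)/(0.50/0.50) = 1.27. Over shares of 50% to 100% it is 0.67 to 1.50; with 60% against 20% documentation it is 0.44 to 2.25. Record visit type and pre-specify a sensitivity analysis restricted to well-care visits. That restriction does not remove the difference between consenting participants and consecutive patients, which should be reported as a limitation.
2. *Four practices.* Report a pilot estimate with practice-level uncertainty, for example from the change in each practice (2 degrees of freedom, t critical value 4.30). The smallest two-sided randomisation p is 2/6 = 0.33, or 2/4 = 0.50 if one practice per city was randomised, which section 6.2.1 does not say.

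The cost is a change of wording and one visit-type field, taken from the EHR or the data-repository request or added to the review form. The 14 Appendix E items are scored "Response options: Met? Yes or No" and none records visit type. No extra charts are needed. The change restores a defined estimate, but not a usable significance test.

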## 5. Specific Aims:

**Aim 1:** Develop and deploy an electronic short screening tool for tobacco and nicotine product use into pediatric primary care workflow in conjunction with 1) clinician and office staff training on the 6As and parent screening through the use of trained Clinical Practice Facilitators (CPFs), 2) clinician-engaged adaptations of the intervention to fit their practice workflow, and 3) support for Maintenance of Certification (MOC) to engage pediatricians in implementing the best practices.

[figure not shown]
**Aim 2:** Gather pilot data about the effectiveness of the intervention on clinician adherence to best practices and changes in practice capacity for change, adaptive reserve, and clinician self-efficacy.

**Aim 3:** Examine the congruence between documentation of the intervention in the EHR and youth report of the intervention.

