*Your practice has agreed to participate in the research study entitled 'The OneFlorida Cancer Control Alliance: Implementing the 6As in Pediatric Primary Care'. The study is intended to learn about assessing adolescents' tobacco use in the clinic and improving patient-doctor communications about tobacco use. This study is supported by the Florida Department of Health James and Esther King Biomedical Research Program, with [name] serving as the Primary Investigator.*

*We are asking the Medical Director and/or Office Manager of each participating practice site to complete a survey about the overall practice structure. The brief confidential survey should take approximately 15 minutes to complete. By completing this survey, you are agreeing to participate in this study. Your responses will be analyzed and presented in aggregate. Your participation in this research study is completely voluntary.*

*You should be able to complete the survey in one sitting. Please fill out the attached paper survey and return it by U.S. mail it using the envelope provided (do not put your name on the survey or your return address on the envelope).*

*Thank you in advance for your help in this work. Please feel free to contact our study coordinator, [name], at [contact] should you have any questions about this letter or the study.*

*Sincerely,*

*[name],*

*OneFlorida Clinical Research Consortium*

*Thank you for agreeing to participate in this survey.*

*We are interested in learning more about your experiences in screening and referring children and adolescents for tobacco and other nicotine product use.*

We are also interested in learning more about the barriers you face in screening and referrals.

This questionnaire also includes items about how your practice is organized and the strategies you use when you want to implement a new intervention.

Appendix A is to be completed by each clinician participating in the study. Appendix B is to be completed by the Medical Director and there needs to be only one completed Appendix B per practice.

**Section 1: One Florida Clinician Survey (complete for each clinician participating in the study) (Add Code for practice site)**

1. What is your terminal degree or primary professional degree?
  - a. Medical degree
  - b. Nursing degree/diploma
  - c. Allied professional diploma in respiratory science/radiation technology, etc.
  - d. Other (specify)
  
2. How would you describe your primary work setting?

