## Appendix B. Adaptive Reserve and Change Process Capability Questionnaires

### B.1 Practice Structure

1. Approximately how often do the clinicians and staff at your practice site **hold meetings** to discuss the practice site's performance on:

*Check (✓) one for each of the following listed meeting topics:*

*(Response options: Never, Annually, Quarterly, Monthly, More often than monthly)*

- a. Overall pediatric quality of care?
- b. Patient satisfaction ratings?
- c. Productivity?
- d. Utilization or costs of care?
- e. Clinician or staff satisfaction?

2. Does your practice monitor the clinician(s) personal performance on ...

*(Response options: No, Yes, Don't know)*

- a. Overall pediatric quality of care
- b. Patient satisfaction ratings? (e.g., patient experience surveys)
- c. Productivity? (e.g., patient volume, procedure volume)
- d. Utilization or costs of care?

3. Does your practice monitor staff members' personal performance on...

*(Response options: No, Yes, Don't know)*

- a. Overall pediatric quality of care
- b. Patient satisfaction ratings? (e.g., patient experience surveys)
- c. Productivity? (e.g., patient volume, procedure volume)
- d. Utilization or costs of care?

4. Do the clinicians at your practice site use planned communications (e.g., letters, phone calls, text messages) to contact patients who are due for preventive care visits

*(Response options: No, Yes, Don't know)*

5. Does your practice site have:

*Check (✓) one for each of the following listed items:*

*(Response options: No, Yes, Don't know)*

- a. Agreements with community service agencies (e.g., health departments) to enhance services for any of your patients?
- b. A referral system for linking your patients to tobacco cessation programs

6. During a typical day in clinic, how often do providers use a computer or other electronic device (e.g., tablet, smart phone) to look up information about the patients they are seeing?

*Check (✓) one:*

- a. Never
- b. Rarely
- c. Sometimes
- d. Usually
- e. Always

7. Does your practice have an electronic medical record?
  - a. No
  - b. Yes
  
8. Does your site utilize an electronic medical record (EMR or electronic health record (EHR)?
  - a. Yes
  - b. No
  
9. If YES, please select the vendor of your practice's EHR:
  - a. Allscripts
  - b. CERNER
  - c. eClinicalWorks
  - d. eMD
  - e. EPIC
  - f. GE Healthcare Centricity
  - g. McKesson
  - h. NextGen
  - i. Practice Partner
  - j. Care360
  - k. Practice Fusion

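### The practice-level ANCOVA in section 6.2.5 has four records and one residual degree of freedom, names no capacity-for-change or adaptive-reserve score, and leaves self-efficacy without an analysis

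*Combined protocol and SAP*

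**What the plan says.** Section 5 gives Aim 2 as gathering pilot data on clinician adherence and on "changes in practice capacity for change, adaptive reserve, and clinician self-efficacy".

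The design is small at practice level. Section 6.2.1: "This study will be implemented with a convenience sample of 4 pediatric primary care practices". On allocation: "Two will be randomly assigned to receive the intervention and two will serve as the comparison groups". The introduction to the surveys, ahead of the clinician questionnaire, says that "there needs to be only one completed Appendix B per practice".

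The second paragraph of section 6.2.5 takes practice characteristics from the CPCQ and the Adaptive Reserve Questionnaire (Appendix B). On timing: "We will collect the practice characteristic data twice, once at baseline and once at 9 months". It then specifies ANCOVA with practices as independent units and group as the predictor of interest. The variables it names are given in one sentence: "The characteristics include meeting frequency, clinician/staff performance evaluation, and planned communication". The diagnostics follow: "We will perform residual analysis to check the normality assumption of the models", with a Box-Cox transformation if normality fails.

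Section 6.2.3 (item A) has each participating clinician complete the Appendix A survey at baseline and at 9 months. Section 6.2.5 contains no analysis of that survey.

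**The concern.** An ANCOVA with diagnostics reads as a plan for a group comparison with p-values. With one record per practice there are only four outcome values, so it is doubtful that the model can estimate its own error variance, let alone show a group effect or check an assumption.

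It is also unclear what is being modelled. Aim 2 speaks of capacity for change, adaptive reserve and self-efficacy. The variables named in the analysis are of another kind: frequency of meetings, performance monitoring and planned contact with patients.

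If the plan is followed, the practice-level results will almost certainly be non-significant whatever happened in the practices. A reader could mistake that for evidence of no change. The self-efficacy data would be collected twice with no stated use.

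**Working it through.** The documents give no power, significance level, SD or degrees of freedom for this analysis, so there is no planned figure to reproduce.

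**Inputs from the documents.** Practices: 4, allocated 2 and 2 (section 6.2.1). Appendix B forms per practice at each time: 1 (survey introduction). Times: baseline and 9 months (section 6.2.5).

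**Assumptions.** One baseline covariate per model, which is the usual ANCOVA; two-sided 5% test; a continuous, normally distributed score; effects in units of the between-practice SD; correlation between baseline and 9 months of 0 to 0.7.

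**1. Degrees of freedom.** Residual df = records − parameters.
- Intercept + group + baseline: 4 − 3 = 1; critical t = 12.71.
- Intercept + group only: 4 − 2 = 2; critical t = 4.30.
- Adding a group-by-baseline interaction, or city, to the first model: 4 − 4 = 0, so no test exists.

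The large-sample critical value, for comparison, is 1.96.

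**2. Power and precision of the 1-df model** (simulation, 100,000 replicates per cell):

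| True difference | Correlation 0 | 0.5 | 0.7 |
|---|---|---|---|
| 0 | 4.9% | 5.0% | 5.1% |
| 1 SD | 6.5% | 6.9% | 7.9% |
| 2 SD | 10.2% | 11.7% | 13.9% |
| 3 SD | 14.8% | 17.1% | 20.4% |
| 5 SD | 24.1% | 27.8% | 33.2% |

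The median width of the 95% confidence interval is about 22, 19 and 16 SD respectively. Power of 80% needs a difference of roughly 15 to 23 SD. Dropping the baseline (2 df) gives 22% power at 2 SD and needs about 5.7 SD for 80%.

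**3. Randomisation test as an alternative.** There are C(4,2) = 6 possible allocations, so the smallest two-sided p is 2/6 = 0.33. If randomisation were within city, which the documents do not state, there would be 4 allocations and the smallest p would be 2/4 = 0.50.

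**4. The residual check.** Let d1 be half the baseline difference between the two intervention practices, and d0 the same for the two controls. Residuals must sum to zero within each group, so they have the form (a, −a, b, −b). They must also be orthogonal to baseline, so a·d1 + b·d0 = 0. Hence they are always proportional to (d0, −d0, −d1, d1). The 9-month answers determine only sign and scale. Three random outcome vectors on one fixed design confirmed this: each gave ±(0.3439, −0.3439, −0.6178, 0.6178) after standardising. A normality check on this pattern describes the baseline values and says nothing about the distribution of the outcome, so it gives no basis for deciding on Box-Cox. For a single item with two observed values, a Box-Cox transformation only relabels them.

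**5. Named variables against Aim 2.**
- Meeting frequency corresponds to Appendix B.1 question 1: five sub-items on a five-level ordered scale.
- Performance evaluation corresponds to questions 2 and 3: eight sub-items, answered no/yes/don't know. Question 2, for example, begins "Does your practice monitor the clinician(s) personal performance on".
- Planned communication corresponds to question 4: one item, no/yes/don't know.
- None of these is in the CPCQ (Appendix B.2). No CPCQ or adaptive-reserve score is defined, although CPCQ items 1c and 1g are negatively worded and N/A is allowed. No rule is given for coding don't know.
- Appendix B has adaptive reserve in its title but no section under that name.
- Section 6.2.3 (item B) says the practice survey assesses physician self-efficacy. Appendix B.1 has no such items; the matching content (current practices, barriers, opinions) is in Appendix A, which section 6.2.5 does not analyse.

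**The case against.** The strongest reply is that this is a pilot. Practice capacity is introduced in the Background as a secondary interest, and section 6.2.5 sets no significance level or decision rule for it. That stands as far as it goes, and the harm from a misread null result is a risk, not something the documents predict. But the paragraph specifies a model with a group effect and diagnostics, and pilot status argues for description in its place.

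A reader might infer that the plan analyses Practice Structure items in place of the Aim 2 outcomes. The documents do not support that. The same paragraph names the CPCQ and the Adaptive Reserve Questionnaire as sources, its list of variables is open-ended, and the Background counts capacity for change and adaptive reserve among the practice characteristics. Appendix B.1 may itself be this protocol's adaptive-reserve form, since section 6.2.3 says that form covers organisational structure. What remains is that no score is named or defined.

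Nor is it established that items would be analysed one at a time. Two of the three named characteristics cover several items and could be composites, so the relabelling remark certainly applies only to planned communication. The power figures likewise describe a continuous score and do not transfer to single ordered or yes/no items. Four records and 1 df apply either way.

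**Conclusion.** The point holds for the practice-level model. With four records and 1 residual degree of freedom, the group test is close to uninformative: power is 6.5% to 7.9% at 1 SD and 10% to 14% at 2 SD, against a 5% false-positive rate. The planned normality check cannot work. The degree of freedom is derived on the assumption of a single baseline covariate; the power figures also assume a continuous normal score and a two-sided 5% test, and the conclusion is the same across correlations of 0 to 0.7. Separately, the plan names no capacity-for-change or adaptive-reserve score as a dependent variable and has no analysis of self-efficacy.

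A reader might go further and conclude that Aim 2 as a whole cannot be answered. That does not follow. Clinician adherence is part of Aim 2, has its own record-level model in section 6.2.5 and is not touched by this point. The aim is worded as gathering pilot data, which description can serve. The limit is on inferential comparison of the practice-level components.

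**What to change.** - Delete the ANCOVA, residual-analysis and Box-Cox steps for practice data.
- Name the CPCQ and adaptive-reserve scores, state which Appendix B items form each, and give the direction of scoring and the handling of N/A and don't know.
- Tabulate the baseline value, 9-month value and change for each of the four practices. Report the remaining B.1 items as description, and make no significance claim.
- Add a descriptive summary of the clinician survey by practice for self-efficacy. First reconcile section 6.2.3 (item B), which places physician self-efficacy in the practice survey, with Appendix A, which holds the matching questions.
- Put a non-identifying clinician study code on Appendix A so that each clinician's two surveys can be paired. At present the form calls only for a practice-site code, and the cover letter asks respondents not to give names. Surveys returned without a code cannot be paired later.

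Cost: analysis-plan wording, the score definitions, the code, and a small change to the survey's confidentiality wording. The plan loses p-values for practice characteristics, which four practices could not support.
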